Methodology: *Criteria:* We will recruit couples where the Veteran partner is positive on VA primary care mental health screens who self-identify as in a committed relationship where one partner demonstrates significant relationship dissatisfaction. We will exclude partners with common contraindications for couples therapy or who are already engaged in family services. *Evaluation:* Partners will provide initial ratings of outcomes in separate baseline sessions. *Intervention:* Then couples will complete BRC in three 30-minute couple sessions. *Follow-up:* Partners will complete post-treatment assessments separately that include outcome measures packet and an open-ended interview.

Data Safety Monitoring Plan: This is a small pilot trial that will not use a data safety monitoring board. Safety will be monitored by the PI, Syracuse VA IRB, and Canandaigua Research Compliance Office (RCO) in consultation with the Information Security Officer (ISO).

Data Analysis: We will use descriptives (e.g., frequencies; means) and repeated measures ANOVA to analyze quantitative data. We will use framework-guided rapid analysis to analyze open-ended qualitative data.

List of Abbreviations

AUDIT-C – Alcohol Use Disorders Identification Test Consumption Questions

BRC - Brief Relationship Checkup

CDGA- Canandaigua VA Medical Center

C-SSRS - Columbia Suicide Severity Rating Scale

Doc # - Reference document Attached to IRB Application Package

EBP – Evidence Based Program

IBCT - Integrative Behavioral Couple Therapy

IPV – Intimate Partner Violence

ISO - Information Security Officer

MI – Motivational Interviewing

PC-MHI – Primary Care Mental Health Integration

PC-PTSD-5 – Primary Care PTSD Screener for DSM-5

PC-Screen – Primary Care Mental Health Screen (i.e., PHQ-2; PHQi9; AUDIT-C; PTSD-PC-5)

PHQ-2 – Physician Health Questionnaire 2-item Depression Screen

PHQi9 – Physician Health Questionnaire, Item 9 Suicide Ideation Screen

RC Questionnaire - Relationship Checkup Questionnaire

RCT - Randomized Control Trial

ROPC- Rochester Community Based Outpatient Clinic

VINCI – VA Informatics and Computing Infrastructure (VINCI)

VVC - VA Video Connect

Contents

Pro	otocol Title:	5
1.0	Study Personnel	5
2.0	Introduction	6
3.0	Objectives	7
4.0	Resources and Personnel	8
5.0	Study Procedures	9
5.	5.1 Study Design	9
5.	5.2 Recruitment Methods	14
5.	5.3 Informed Consent Procedures	16
5.	5.4 Inclusion/Exclusion Criteria	17
5.	5.5 Study Evaluations	18
5.	5.6 Data Analysis	19

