Participation risk. Study procedures do not expose the participants to physical risk beyond those encountered in daily life but may expose them to psychological distress and fatigue. The assessments, semi-structured interviews, and intervention sessions encourage participants to recall personal events, life stressors, and suicide-related issues that may evoke distress. Discussion of these topics in front of a partner during couple therapy sessions may lead to additional stress or increased conflict.

Confidentiality risk. The sharing of personal and sensitive information increases the potential that research staff may need to break confidentiality in the event that a participant is determined to be a risk to self or others, or child abuse or neglect is revealed.

Measures to Protect from Risk

Protections to minimize population risk. Exclusion criteria will ensure that participants at highest likelihood for a negative response to treatment (i.e., those reporting severe IPV such as IPV with injury or sexual violence in the year prior to the study; those reporting ideation with

intent or attempt in the month prior to the study) and those unlikely to benefit from treatment (e.g., lack of comprehension of consent; psychosis; mania) will be excluded from the study. Additionally, all staff will be trained in the semi-structured IPV interview, C-SSRS, P4, and MINI psychosis and mania scales to be used at any time they are concerned about individual functioning during either in-person sessions or phone sessions.

Protections to minimize participation risk. Recruitment and informed consent procedures were designed to ensure patients do not feel like participation is required and feel able to discontinue at any time, including if they find themselves unduly stressed by participation. Participants will be explicitly reminded about their right to withdraw participation during verbal consent to initiate screening, after completion of screening but before engaging in baseline, and upon completing full consent form during baseline. Patients unable to understand the informed consent process will be excluded from participating. Participants demonstrating active psychosis or mania will be excluded due to potential that participation in couples treatment could increase distress.

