completed transcripts become available, approved study staff will move these files from the transcription folder into another folder that is only accessible to IRB-approved study staff and password protected, where they will be stored for qualitative analysis. RA templates will summarize transcripts on specific BRC elements. These will be consolidated into themes that can inform BRC refinement (Sub-aim 3-2). RA yields insights comparable to more intensive coding using less staff resources.⁵⁸

Exploratory analyses. Due to a lack of prior literature on relationship-focused interventions impacting risk factors beyond depression, we do not have any specific aims or directional hypotheses. However, we will calculate separate Cohen's *d* estimates by partner using the same analytic approach seen in Sub-aim 2-2. Additionally, we will compare outcomes across higher and lower-functioning couples. The analyses will help evaluate the BRC's tolerability and safety, adding additional considerations for changes in the RCT.

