6.0 Reporting

Unanticipated problems

Study staff will report any unanticipated problems to the PI and study coordinator via encrypted e-mail and/or phone call. All problems will be documented using internal logs saved locally behind the VA firewall.

Unanticipated problems that do not significantly impact the experience of participants or result in a deviation from the study protocol will be noted and provided to the IRB in annual report. Recurring problems will form the basis for amendments in order to improve Veteran and family member experiences, improve data quality, and/or minimize the impact on clinical care activities within referring clinics.

Per IRB regulations, problems or events resulting in a deviation from the study protocol (e.g., emergency hospitalization to address suicidal behaviors) will be reported to the PI within 24 hours and to the IRB in 48 hours using required IRB forms.

Adverse events

All internal serious adverse event reports will be sent via encrypted e-mail to the PI and Study Coordinator. Copies of all SAE reports (both IRB forms and internal study forms) will be saved locally behind the VA firewall. No paper copies will be saved. Adverse events will include all suicide attempts, reports of new intimate partner violence behaviors (of any severity) after the initial screening, and occurrences of imminent risk. Per IRB regulations, any serious adverse event, any event resulting in a deviation from the study protocol (e.g., emergency hospitalization to address suicidal behaviors) or death will be reported to the PI within 24 hours and to the IRB in 48 hours. This will be completed in order to assess significance and determine an appropriate response. Adverse events that involve temporary distress will be noted by interviewers and provided to the IRB in an annual report.

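### Section 5.6 ties tolerability and safety to mean effect sizes and names no count of adverse events, safety withdrawals or partners who worsen

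*Combined protocol and SAP*

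**What the plan says.** The only mention of safety or tolerability in section 5.6 is in its Exploratory analyses paragraph. Two analyses are named there:

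- separate Cohen's d "estimates by partner using the same analytic approach seen in Sub-aim 2-2";
- a subgroup contrast: "we will compare outcomes across higher and lower-functioning couples". No cut-off or scale defines the two groups.

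The paragraph then says these analyses will help evaluate "tolerability and safety, adding additional considerations for changes in the RCT".

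The harms themselves are dealt with in section 6.0: "Adverse events will include all suicide attempts, reports of new intimate partner violence behaviors (of any severity) after the initial screening". Imminent risk is on the same list. Serious events go to the PI within 24 hours and the IRB within 48 hours, and the purpose given is: "This will be completed in order to assess significance and determine an appropriate response". For milder events: "Adverse events that involve temporary distress will be noted by interviewers and provided to the IRB in an annual report". The abstract adds: "This is a small pilot trial that will not use a data safety monitoring board". Monitoring rests with the PI, the IRB and the research compliance office.

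Section 5.6 gives no count, rate, listing or interval for any of these events. The same is true of the one-item violence screen at each session, the follow-up violence assessment and the reasons for withdrawal (sections 5.1, 5.5 and 5.7).

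**The concern.** A pre-post d describes the average partner who returned a follow-up score. Tolerability and safety turn on the partners who did badly, including those who left because they did badly. Three features of this plan make the gap matter.

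- Section 2.0 states that BRC is untested in Veterans and in samples where a partner has significant mental health concerns.
- Section 5.1 expects that discussing sensitive topics in front of a partner "may lead to additional stress or increased conflict".
- Section 5.6 says the exploratory analyses will add considerations for the RCT and that findings will feed a grant application and possibly publications.

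Reports to the IRB carry no denominator and no rate. A reader of the pilot's results could therefore see a favourable mean and have no summary of how many couples had an event or how many partners deteriorated.

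**Working it through.** **Inputs from the documents.** 20 couples, single arm (abstract); 75% retention (section 5.6); d computed separately for Veterans and Supporting Partners (section 5.6). The documents give no individual changes and no event rates, so those below are assumptions. Change is coded so that positive means improvement, in SD units.

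**1. The plan's own figure.** 20 × 0.75 = 15 couples with complete data, as section 5.6 states. Each role therefore contributes about 15 partners to a pre-post d.

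**2. Can the mean hide a worsening minority?** Mean change = [(15 − k) × benefit − k × harm] / 15, where k partners worsen.

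- k = 3, benefit 0.6, harm 1.0: (12 × 0.6 − 3 × 1.0)/15 = 4.2/15 = **+0.28**.
- k = 3, benefit 0.5, harm 1.0: (6.0 − 3.0)/15 = **+0.20**.
- Over k = 1 to 4, harm of 0.5 or 1.0 and benefit of 0.3 or 0.5, the mean runs from −0.05 to +0.43. It is negative in only one of the 16 cases (k = 4, harm 1.0, benefit 0.3).
- Standardising by the SD of change does not help. In the first example that SD is √[(12 × 0.32² + 3 × 1.28²)/14] = √(6.144/14) = 0.66, so d = 0.28/0.66 = 0.42.

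**3. Who is left out of the mean?** Under section 5.7, an involuntary withdrawal (for example for extreme distress) while an in-person session is scheduled removes both partners and cancels their study activities. They then have no follow-up score. Suppose 3 of 20 partners in one role lose 1.0 SD and 17 gain 0.5 SD.

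- All 20: (17 × 0.5 − 3 × 1.0)/20 = 5.5/20 = **+0.275**.
- If those three are among the five expected to be lost, the 15 observed give **+0.50**.

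**4. Do the section 6.0 events reach d by another route?** Table 1 labels the violence measures as safety or exclusion measures, not as Aim 2 or risk measures. The exclusion interview covers the last year and the follow-up assessment one month, so a pre-post difference would not compare like with like. The C-SSRS attempt items are labelled for risk as well as safety and might be taken into the exploratory set. But section 5.4 excludes anyone with an attempt in the last month, so that baseline count is zero by design. A d standardised by baseline SD is then undefined, and a follow-up count is the informative summary.

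**5. What would a count show?** Exact two-sided 95% intervals, assuming all 20 couples start BRC:

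| Couples with an event | 95% CI |
|---|---|
| 0/20 | 0 to 16.8% |
| 1/20 | 0.1 to 24.9% |
| 2/20 | 1.2 to 31.7% |
| 3/20 | 3.2 to 37.9% |

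For 0/20 the upper limit is 1 − 0.025^(1/20) = 16.8% (one-sided: 1 − 0.05^(1/20) = 13.9%). If only 15 couples were counted, 0/15 would allow up to 21.8%. At a true couple-level rate of 5%, the chance of seeing at least one affected couple in 20 is 1 − 0.95^20 = 64%.

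**The case against.** The best reply is that the plan claims little. The text says the analyses will help evaluate safety. Safety is not one of the three aims, no safety criterion is set, and this is a pilot sized by staff capacity. A reader might infer that BRC will be declared safe on the strength of a mean effect size. The documents do not say that, and the point here does not depend on it.

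A reader might also infer that harm would go unnoticed. That is not supported either: serious events reach the PI and IRB individually and quickly, and section 5.1 requires immediate referral for risk concerns disclosed at follow-up.

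Nor are withdrawals wholly ignored. The completion rate in Sub-aim 1-2 falls with each one, though without the reason. Partners who withdraw voluntarily from treatment may still give follow-up data, so step 3 applies to some withdrawals and not all. The acceptability rule in Sub-aim 3-1 is a proportion, the interviews may bring out bad experiences, and the abstract promises descriptives in general terms. None of these names an adverse event, a denominator or a period.

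The examples in steps 2 and 3 use invented changes. They show that masking is possible, not that it is likely. They concern partners within a role, so they do not show that a fifth of couples worsened. The intervals in step 5 reflect 20 couples under any method and are not evidence that d is the wrong statistic.

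What stands is that section 5.6 gives safety a purpose, attaches it to statistics that are poor at detecting harm, and names nothing better.

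**Conclusion.** The point holds in a limited form. The analysis that is meant to help evaluate tolerability and safety, and to inform the RCT, rests on mean change and an undefined subgroup contrast. The section 6.0 events and withdrawals for distress have no named place in it. Under the assumed changes, a mean of +0.20 to +0.28 SD is compatible with 3 of 15 partners in a role (20%) losing a full SD. Loss of the harmed partners could raise an observed d from +0.275 to +0.50.

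This is a gap in the planned summary, not in real-time oversight, and it alters no stated aim or decision rule. It is still worth closing, because the information is collected anyway and a count is a plainly better summary.

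The personnel and resources sections (1.0 and 4.0) were not available, and the Safety entry in section 5.5 breaks off mid-sentence in the text reviewed. Nothing has been inferred from either.

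**What to change.** In section 5.6, base the tolerability and safety summary on two descriptive displays.

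1. **Events.** Give the number and percentage of couples, and of partners, with each type of section 6.0 adverse event and with each withdrawal for distress or safety. Put exact 95% intervals on the couple-level percentages.
   - For events before Session 1, the denominator is all couples completing baseline.
   - For events from Session 1 to the end of follow-up, it is all couples starting BRC.
   - Do not split the period further. The follow-up violence assessment looks back one month from an interview held up to 30 days after the last session, so it cannot place events before or after Session 3.
2. **Individual worsening.** Give, by role, the number of partners who worsen from baseline on CSI, PHQ-9, PHQ item 9 or C-SSRS ideation, using thresholds fixed before analysis. Examples are any increase on item 9 or the C-SSRS, and a stated reliable-change criterion or 0.5 baseline SD on CSI and PHQ-9. Show beside each the number of partners without follow-up, since the counts are minimums when data are missing.

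Keep Cohen's d and the higher/lower-functioning comparison as descriptions of outcome only.

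The cost is one extra table and a few sentences, with no new data collection. The downside is that the intervals will be wide and will show openly that 20 couples cannot establish safety.

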5.7 Withdrawal of Subjects

Voluntary withdrawal

Process for withdrawal. All couple-based treatment sessions will require consent from both partners before proceeding. Individual participants may request to withdraw from participating in the study at any time by contacting study staff. Study staff will ask for a brief reason for voluntary withdrawal to monitor for potential adverse events. If staff is concerned about safety, they will conduct follow-up assessments as appropriate based on their concerns (e.g., IPV interview, P4 suicide risk screener, MINI mania/psychosis screen) and follow the appropriate protocol.

Withdrawal of one partner during treatment. As this is a pilot of a couples treatment, if either partner withdraws during the treatment process, then the other partner will not be able to complete the treatment. Partners will be reminded of this fact and will be offered the opportunity to withhold their decision to withdraw if they would like to discuss their choice with a partner first (with a member of study staff following up after participating). However, partners are NOT REQUIRED to take this time in order to withdraw.

If a participant withdraws while the couple has an in-person session scheduled, study staff will explain that they need to notify the partner of this decision and the cancellation of ongoing appointments. Withdrawal from the intervention will not impact either participant's ability to participate in the follow-up assessment, which will allow either partner to give feedback on what was appealing,

If a participant withdraws after completion of the treatment process (i.e., not wishing to participate in the follow-up assessments), the partner will not need to be informed, as all remaining study activities (assessment packet, interview process) are completed individually.

Involuntary withdrawal

Safety of participants/couple. Exclusion criteria was selected to minimize the likelihood that the intervention would negatively impact either partner. However, consistent with standard approaches in VA intervention research, we will withdraw participants due to unanticipated circumstances, such as extreme distress from participating in the intervention or if we judge the participation of the couple is not in their best interest. Any such decisions will be documented using the reporting guidelines (Section 6.0).

If this occurs while the couple has an in-person session scheduled (baseline or joint checkup session), study staff will withdraw both partners from the study and will notify both partners of this decision and the cancellation of ongoing study activities.

If a participant withdraws after completion of the treatment process (i.e., a situation where the follow-up interviews may be contra-indicated), decisions about withdrawal will be made separately for each partner as all remaining study activities (assessment packet, interview process) are completed individually. Participants will not need to be informed of whether or not their partner was withdrawn from the study in this manner.

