If study staff are concerned about risk during a VVC session (e.g., VVC baseline; VVC treatment sessions; VVC follow-up assessment), we will enact risk management procedures consistent with national telehealth guidelines. Specifically, these guidelines require that study staff will verify and/or update necessary patient information at the beginning of each telehealth session (i.e., current location, patient's phone number; contact information of emergency support if available; and local emergency # if different than 911). This will allow the interviewer to both develop technology contingencies with the couple (e.g., in case of poor connection) or respond to physical or mental health emergencies. The VVC service includes a specific enhanced-911 service (E911) that is prepared to respond to medical emergencies or mental health emergencies occurring during telehealth sessions. If patients are determined to be at imminent risk for suicide during a session, the interviewer will utilize this E911 service, which has established procedures for locating callers and initiating rescues in collaboration with local emergency services. E911 also has mental health responders trained to respond to suicidal crises. Interviewers will try to elicit agreement for necessary services and will always inform patients that they are seeking additional care if the patient refuses to cooperate. We will disclose to the responder any information that bears directly on risk (e.g., level of risk, suicide plan, access to a weapon, prior attempts, etc.). As with in-person sessions, study clinical staff

will be accessible to provide guidance to research staff and interventionists about appropriate risk determination as well as treatment.

Protection against IPV risk. Our IPV risk management procedure is consistent with VA guidance for couples therapy (which advises that the best time to initially screen for IPV is during individual in-person sessions and then every subsequent contact) IPV Assistance Program guidelines (which takes a person-centered approach to deciding on the next course of action). Accordingly, violence will first be systematically assessed during the Baselines, which are conducted separately and maximize each partner's assurance of privacy and confidentiality. After that, all sessions will contain the 1-item self-report IPV screen used as a default in session packets in VA couples therapies.

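### On its natural reading, Section 5.7 ends follow-up for couples whom staff withdraw during BRC; if any occur and fare worse, the questionnaire-based Aim 2 estimates could lean favourable

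*Combined protocol and SAP*

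**What the plan says.** Section 5.7 of the combined protocol and SAP treats three situations differently.

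- **Voluntary, during treatment.** Leaving the intervention does not affect either person's "ability to participate in the follow-up assessment, which will allow either partner to give feedback on what was appealing" (the sentence breaks off there in the available text).
- **Involuntary, with an in-person baseline or joint session scheduled.** Here "study staff will withdraw both partners from the study and will notify both partners of this decision and the cancellation of ongoing study activities". The example reasons given for involuntary withdrawal are circumstances "such as extreme distress from participating in the intervention or if we judge the participation of the couple is not in their best interest".
- **Involuntary, after treatment.** The decision is made for each partner separately, because "all remaining study activities (assessment packet, interview process) are completed individually". The text describes this case as "a situation where the follow-up interviews may be contra-indicated".

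Section 5.1 allows any or all joint sessions to be held remotely. The involuntary rule names only in-person sessions.

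Section 5.6 bases Aim 2 on pre-post change: a Partner by Time repeated measures ANOVA for relationship quality and intimacy, and Cohen's d by partner role for suicide risk factors and for efficacy in discussing mental health. These effect sizes are to inform power for the later RCT. The exploratory analyses use the same d approach and are meant to help judge tolerability and safety. Section 5.6 names no missing-data method or sensitivity analysis for couples without post-treatment scores.

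**The concern.** Couples whom staff stop during BRC may be among those for whom it went badly. If they also lose the follow-up packet and interview, the pre-post estimates describe couples who tolerated the intervention, and the loss is related to outcome. What would go missing is the set of scheduled post-treatment scores: CSI, PRI, PHQ-9, INQ, and the scheduled C-SSRS and IPV assessments. The estimates passed to the RCT power calculation, and the analyses meant to judge tolerability, could then look somewhat better than they should. Nothing in the reported intervals would show it. Withdrawals at baseline come before any BRC session and are not at issue.

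**Working it through.** **Reading the text.** The voluntary paragraph speaks of withdrawal from the intervention and of cancelled appointments, and it preserves follow-up. The involuntary paragraph speaks of withdrawal from the study and of cancelled study activities, and it contains no such preservation. Section 5.7 twice counts the packet and interview among the study activities still to be done after treatment. Taken together, the natural reading is that follow-up is cancelled too. Nothing elsewhere in the protocol restores it.

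**The plan's own figure (Section 5.6).** 20 couples × 0.75 retention = 15 couples with complete data, as stated. One couple is 1/20 = 5% of those recruited and 1 of the 20 − 15 = 5 expected losses.

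**Sensitivity of d to one omitted couple.** The plan gives no effect size and no rate of staff withdrawal, so these inputs are assumptions: n = 15 observed couples, d = 0.50 (observed SD of change set to 1), and one withdrawn couple whose change is g = 0.5 to 1.5 SD worse than the observed mean.

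- *SD held fixed.* Shift = g/16, which gives 0.5/16 = 0.031 and 1.5/16 = 0.094.
- *SD re-estimated with the couple included.* SD² = (14 + (15/16)g²)/15 and d = (0.50 − g/16)/SD.
  - g = 0.5: SD = √(14.234/15) = 0.974; d = 0.469/0.974 = 0.481; shift 0.019.
  - g = 1.5: SD = √(16.109/15) = 1.036; d = 0.406/1.036 = 0.392; shift 0.108.

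**Against sampling error.** SE of d at n = 15 is √(1/15 + 0.50²/30) = √0.075 = 0.274, so the 95% half-width is 1.96 × 0.274 = 0.537. The shifts are 6% to 17% of this with SD fixed, and 4% to 20% with SD re-estimated.

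**Partial eta-squared for Time (CSI, PRI).** On couple-mean change, with d now taken as the couple-mean value, partial η² = nd²/(nd² + n − 1).

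| Case | n | d | Partial η² |
|---|---|---|---|
| Observed couples only | 15 | 0.50 | 3.75/17.75 = 0.211 |
| Add one couple, g = 0.5 | 16 | 0.481 | 0.198 |
| Add one couple, g = 1.5 | 16 | 0.392 | 0.141 |

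The noncentral-F 95% interval for F = 3.75 on (1, 14) df runs from 0 to about 0.5.

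**More than one couple.** The ranges above are for exactly one couple. With SD fixed, adding k couples moves d by kg/(15 + k). Three couples at g = 1.5 give 4.5/18 = 0.25. With no such couple, or with g = 0, the shift is zero.

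**The case against.** - **The reading is arguable.** Follow-up interviews are arranged only after the final session, so at the time of a staff withdrawal none need be ongoing. The parenthesis listing the packet and interview describes what remains after treatment. A reader might infer that the protocol expressly bars follow-up for these couples; no sentence does. What stands against the objection is that the couple is withdrawn from the study, not merely from BRC.
- **The comparison is not fully like for like.** A reader might infer that every voluntary stopper keeps follow-up. Section 5.7 preserves it for people who leave the intervention, but participants may also leave the whole study.
- **Stopping research contact is a defensible safety choice.** The follow-up asks about suicidal ideation and IPV. This has force, but the protocol already decides case by case, for each partner, after treatment, and the same judgement can be used earlier.
- **Much is already captured.** A reader might infer that safety information is lost. The IPV interview, C-SSRS, P4 and MINI are available "to be used at any time they are concerned about individual functioning"; "all sessions will contain the 1-item self-report IPV screen"; and Section 6.0 states that "Adverse events will include all suicide attempts, reports of new intimate partner violence behaviors (of any severity) after the initial screening". The withdrawal itself is documented, and the couple counts as a non-completer under Aim 1. The gap is in outcome scores, not safety reporting.
- **The effect is small and the direction inferred.** Section 5.7 calls the circumstances unanticipated, and a judgement about a couple's best interest need not reflect harm from BRC. Aim 2 has no test threshold or go/no-go rule. All of this stands and limits the priority.

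**Conclusion.** The point holds as a conditional one. On the natural, though not explicit, reading of Section 5.7, both partners lose follow-up when staff withdraw a couple during BRC with an in-person session scheduled. Those who voluntarily leave only the intervention do not, and remote couples have no rule.

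It would go too far to say that the Aim 2 estimates will be biased upward. That needs at least one such withdrawal, and couples who fare worse than those observed; the documents establish neither. Under the assumed values, one couple moves d by about 0.02 to 0.11, and partial η² falls from 0.21 to between 0.20 and 0.14. Both shifts are well inside sampling error. They also exceed what the fix would recover in the same scenario if contact is contraindicated or refused. The possible lean is confined to outcomes that need post-treatment scores; the Veteran's service use comes from chart review and should be unaffected. This is a cheap improvement of low priority.

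**What to change.** In Section 5.7, for couples who have started BRC in person or remotely:

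1. Separate withdrawal from BRC from withdrawal from the study.
2. When staff end BRC, offer each partner the existing individual follow-up packet and interview unless the licensed psychologists judge contact contraindicated for that person. This extends the per-partner rule that the section already applies after treatment.
3. Report the number of staff withdrawals and their reasons beside the Aim 2 estimates, so that the selection is visible even where no contact is made.

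The clinical decision to stop BRC is unchanged. The cost is protocol wording plus the existing follow-up materials and the $50 follow-up payment per person. The downside is a few extra contacts with distressed participants, each subject to clinical judgement, and some data will still be missing.
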